10.2.1. Humoral Immune Responses

HIV-specific Binding Antibody ELISA Assays will be performed to detect serum or plasma IgG and IgA binding antibodies to HIV-1 gp120, in particular to the V1V2 loops. Capture antigens will include V1V2 sequences from both subtype AE and Subtype B HIV-1 Env (gp70V1V2 92TH023 and gp70V1V2 Case A2), and HIV-1 Env gp120 proteins matched to sequences in AIDSVAX® B/E without the gD tag and with an 11 amino acid N-terminal deletion, represented as gp120 A244gD- D11 and gp120 MNgD- D11. Durability of IgG response will be assessed for each participant by estimating the decline in \log_{10} IgG from peak to 6- and 12-months post vaccination.

Neutralizing Antibody Assays will be measured as a function of reductions in luciferase (Luc) reporter gene expression after a single round of infection in TZM-bl cells using high throughput analysis. Stocks of molecularly cloned envelope-pseudotyped viruses have been prepared by transfection in 293T/17 cells (American Type Culture Collection) and titrated in TZM-bl cells. This assay has been formally optimized and validated and was performed in compliance with Good Clinical Laboratory Practices, including participation in a formal proficiency testing program. Tier 2 neutralization was assessed using a panel of 11 pseudoviruses, and a global panel.

Antibody Profiling will be conducted to assess antibody breadth and correlation of Fc receptor usage with antibody function. The current capacity for Antibody Profiling is the assessment of over 300 samples in one experiment. The beads presenting the HIV antigens will be distributed robotically in a high-throughput manner into 384 well plates. Similarly, the samples will be diluted robotically and incubated with the beads. Detection reagents will be added to the wells after washing. These detection reagents are inclusive of subclass, isotype and Fc receptor usage. Therefore, in one well, we will be able to capture 900 to 1000 data points from a single sample, and over 250,000 data points per experiment that will allow evaluation of the humoral immune response to these vaccine strategies.

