4.7. Immunogenicity Variables

Vaccine-induced immune responses will be assessed in study participants as detailed in the SOE. Humoral responses will be assessed by HIV-specific binding and neutralizing antibody assays at Days 0, 14, 168, and possibly at Day 336. HIV-specific binding antibody responses in the rectal, semen and cervico-vaginal mucosal compartments will be assessed using non-invasive sampling methods (sponge, cup, and masturbation) at Days 0, 14, and 168. Cell-mediated immune responses will be assessed via PBMCs and by utilizing optional invasive sigmoid and lymph node biopsies that will be performed at Day 14, dependent on sample availability. Results of immunology assessments through invasive collection methods in the mucosal compartments are exploratory and will be mostly descriptive as performed in a limited number of participants.

Measurement of CD4+ and CD8+ T-cell effector function will be evaluated through response by cytokines such as IFN- γ and IL2 at Days 0, 14, 168, and possibly at 336. The CD4+ function will also be assessed by the lymphoproliferation responses as measured by the functional CFSE assay at Days 0 and 14. Innate immunity (e.g., NK cells) will be assessed by quantifying ADCC, ADCP and cytokines produced by NK cells at Days 0, 14 and 168, determining innate cells' phenotype and function using various flow cytometric panels at Days 0, 1, 7, and 14, cytokine array assays to characterize the type of cytokines elicited by this vaccine regimen with or without adjuvants, and other related assays. Granulocytes and neutrophils (NET assay) will also be assessed in whole blood at Days 0, 14, and 168.

B-cell responses will be characterized in blood at Days 0, 7, 14, and 168 and in diverse anatomical compartments (provided by sigmoid and lymph nodes biopsies) in a subset of participants, dependent on sample availability.

Leukapheresis will be performed at Day 14 in a subset of willing participants for in-depth investigations of the T-cell responses.

In the context of unknown immune correlates of protection, additional assessments may be performed as new scientific technologies and assessment tools are made available.

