8. IMMUNOGENICITY EVALUATION

8.1. Primary Immunogenicity Analysis

The primary immunogenicity endpoint is the magnitude of plasma IgG (antigen-specific) responses as measured by the endpoint titer, the same variable assessed in RV306. GMTs will be calculated for each group at each visit and the per-participant peak across all visits, along with 95% CIs (exponentiating the CI limits for the log GMT based on the normal distribution). Hypothesis testing is planned for targeted time points; this will be performed in order to aid in interpretation by helping to determine immune responses for potential further examination in future studies. First, group GMTs will be compared across all vaccination groups via ANOVA (null hypothesis that all groups share the same GMT) at the 5%-level, and if that is found to be significant, pairwise comparisons via 2-sided t-tests and the Bonferroni-Holm step-down procedure will be made and a 1% significance threshold will be applied. The two collapsed comparisons will be via 2-sided t-tests of log-GMTs at the $\alpha=0.025$ -level. If the data appear especially non-normal, nonparametric testing will be considered instead.

The reverse cumulative distribution (RCD) of titers (with endpoint titer on the x-axis and the proportion of participants with at least that titer on the y-axis) at each visit will be shown by vaccination group, separately for each antigen.

Seroconversion or seropositivity post-vaccination will be defined based on criteria given by the performing lab, and the number and percent of participants in each group achieving seroconversion/seropositivity at each visit will be presented along with the associated exact 95% Clopper-Pearson CI. The same group comparisons will be performed, via exact binomial tests and the same handling of significance and multiplicity.

Immune response over time (durability) will be assessed by the positive incremental area under the curve (AUC) based on a graph with log endpoint titer on the y-axis and visit day on the x-axis. For comparability between participants with different numbers of samples (visits) available, these values will be scaled by the week of the last available sample. If no sample is available for visits other than the first and last, no explicit imputation will be done, and the AUC will be calculated based on available samples. Log AUC will be analyzed similarly to the visit-by-visit titers.

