The week of peak response will also be described by vaccination group, with no hypothesis testing planned. If, by chance, there are equivalent peak responses at two visits, the first will be considered the peak.

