Participant Disposition	Full IHV01/A244 (N=X)		Fractional IHV01/A244 (N=X)		Full IHV01/A244 + ALFQ (N=X)		Fractional IHV01/A244 + ALFQ (N=X)		Placebo (N=X)		All Participants (N=X)	
	n	%	n	%	n	%	n	%	n	%	n	%
Screened	--	--	--	--	--	--	--	--	--	--	x	--
Enrolled/Randomized	x	100	x	100	x	100	x	100	x	100	x	100
Received Study Vaccination (Visit 1, Day 0)	x	xx	x	xx	x	xx	x	xx	x	xx	x	xx
Completed Visit 2 (Day 1)	x	xx	x	xx	x	xx	x	xx	x	xx	x	xx
Completed Visit 3 (Day 7)	x	xx	x	xx	x	xx	x	xx	x	xx	x	xx
Completed Visit 4 (Day 14)	x	xx	x	xx	x	xx	x	xx	x	xx	x	xx
Completed Visit 5 (Day 168)	x	xx	x	xx	x	xx	x	xx	x	xx	x	xx
Completed Follow-up (Visit 6, Day 336)	x	xx	x	xx	x	xx	x	xx	x	xx	x	xx
Completed All Scheduled Blood Draws	x	xx	x	xx	x	xx	x	xx	x	xx	x	xx

Note: N = Number of randomized participants

Table 6: Summary of Categorical Demographic and Baseline Characteristics by Site

Variable	Characteristic	[Site 1] (N=X)		[Site 2] (N=X)		All Participants (N=X)		p-value
		n	%	n	%	n	%	
Age	20-29	x	xx	x	xx	x	xx	0.xx
	30-39							-
	40-49							-
	50+							-
Sex	Male							0.xx
	Female							-
Level of Education	Primary school							0.xx
	Secondary school							-
	Vocational							-
	Bachelor degree							-
	Higher than bachelor degree							-
Occupation	No occupation							0.xx
	Student							-
	Government employee							-
	Private sector employee							-
	Merchant/Self-employed							-
	Agriculturist/Farmer							-
	Other							-
Note: N = Number of randomized participants. Exact binomial test used to compare variables between sites.								

Table 7: Summary of Continuous Demographic and Baseline Characteristics by Site

Variable	Statistic	[Site 1] (N=X)	[Site 2] (N=X)	All Participants (N=X)	p-value
Age	Mean	xx	xx	xx	0.xx
	Standard Deviation	xx	xx	xx	-
	Median	xx	xx	xx	-
	Minimum	x	x	x	-
BMI	Maximum	x	x	x	-
	Mean	xx	xx	xx	0.xx
	Standard Deviation	xx	xx	xx	-
	Median	xx	xx	xx	-
	Minimum	x	x	x	-
	Maximum	x	x	x	-
Note: N = Number of randomized participants. t-test used to compare variables between sites.					

Table 8: Summary of Categorical Demographic and Baseline Characteristics by Vaccination Group

Variable	Statistic	Full IHV01/A244 (N=X)		Fractional IHV01/A244 (N=X)		Full IHV01/A244 + ALFQ (N=X)		Fractional IHV01/A244 + ALFQ (N=X)		Placebo (N=X)		All Participants (N=X)	
		n	%	n	%	n	%	n	%	n	%	n	%
Age	20-29	x	xx	x	xx	x	xx	x	xx	x	xx	x	xx
	30-39												
	40-49												
	50+												
Sex	Male												
	Female												
Level of Education	Primary school												

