gp120 MNgD- D11	xx	xx.x (xx.x, xx.x)	xx	xx.x (xx.x, xx.x)	xx	xx.x (xx.x, xx.x)	xx	xx.x (xx.x, xx.x)	xx	xx.x (xx.x, xx.x)	0.xx
gp70V1V2 92TH023	xx	xx.x (xx.x, xx.x)	xx	xx.x (xx.x, xx.x)	xx	xx.x (xx.x, xx.x)	xx	xx.x (xx.x, xx.x)	xx	xx.x (xx.x, xx.x)	0.xx
gp70V1V2 Case A2	xx	xx.x (xx.x, xx.x)	xx	xx.x (xx.x, xx.x)	xx	xx.x (xx.x, xx.x)	xx	xx.x (xx.x, xx.x)	xx	xx.x (xx.x, xx.x)	0.xx
[Additional antigens]											

Note: N = Number of participants in the Immunogenicity Population; n = Number of participants with available analysis values

^aANOVA used to compare mean log AUC across all vaccination groups

Table 30: Pairwise Comparisons of Log AUC Between Vaccination Groups by Antigen – [Assay name]

Antigen	Comparison	p-value ^a	Adjusted p-value ^b
gp120A244gD-D11	Full IHV01/A244 vs. Placebo	0.xx	0.xx
	Fractional IHV01/A244 vs. Placebo	0.xx	0.xx
	Full IHV01/A244 + ALFQ vs. Placebo	0.xx	0.xx
	Fractional IHV01/A244 + ALFQ vs. Placebo	0.xx	0.xx
	Full IHV01/A244 vs. Fractional IHV01/A244	0.xx	0.xx
	Full IHV01/A244 vs. Full IHV01/A244 + ALFQ	0.xx	0.xx
	Full IHV01/A244 vs. Fractional IHV01/A244 + ALFQ	0.xx	0.xx
	[Additional pairwise comparisons]	0.xx	0.xx
[Additional antigens]			

^aTwo-sided t-test used to compare log AUC group means
^bStep-down Bonferroni-Holm procedure used

Table 31: Collapsed Comparisons of Log AUC by Antigen – [Assay name]

Antigen	Full IHV01/A244 (N=X)		Fractional IHV01/A244 (N=X)		p-value ^a	ALFQ (N=X)		No ALFQ (N=X)		p-value ^a
	n	Mean (95% CI)	n	Mean (95% CI)		n	Mean (95% CI)	n	Mean (95% CI)	
gp120A244gD-D11	xx	xx.x (xx.x, xx.x)	xx	xx.x (xx.x, xx.x)	0.xx	xx	xx.x (xx.x, xx.x)	xx	xx.x (xx.x, xx.x)	0.xx
[Additional antigens]										

Note: N = Number of participants in the Immunogenicity Population; n = Number of participants with available analysis values

^aTwo-sided t-tests used

Table 32: Geometric Mean Titers and Associated 95% CIs by Visit, Antigen, and Vaccination Group – [assay name]

Visit	Antigen	Full IHV01/A244 (N=X)		Fractional IHV01/A244 (N=X)		Full IHV01/A244 + ALFQ (N=X)		Fractional IHV01/A244 + ALFQ (N=X)		Placebo (N=X)		p-value ^a
		n	GMT (95% CI)	n	GMT (95% CI)	n	GMT (95% CI)	n	GMT (95% CI)	n	GMT (95% CI)	
Baseline (Day 0)	gp120A244gD-D11	xx	xx.x (xx.x, xx.x)	xx	xx.x (xx.x, xx.x)	xx	xx.x (xx.x, xx.x)	xx	xx.x (xx.x, xx.x)	xx	xx.x (xx.x, xx.x)	0.xx
	[Additional antigens]	xx	xx.x (xx.x, xx.x)	xx	xx.x (xx.x, xx.x)	xx	xx.x (xx.x, xx.x)	xx	xx.x (xx.x, xx.x)	xx	xx.x (xx.x, xx.x)	0.xx

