		xx	xx.x (xx.x, xx.x)	xx	xx.x (xx.x, xx.x)	xx	xx.x (xx.x, xx.x)	xx	xx.x (xx.x, xx.x)	xx	xx.x (xx.x, xx.x)	0.xx
[Additional visits or Peak]		xx	xx.x (xx.x, xx.x)	xx	xx.x (xx.x, xx.x)	xx	xx.x (xx.x, xx.x)	xx	xx.x (xx.x, xx.x)	xx	xx.x (xx.x, xx.x)	0.xx

Note: N = Number of participants in the Immunogenicity Population; n = Number of participants with available samples
^aANOVA used to compare log titer group means across all vaccination groups

Note: This will be adapted for assays with continuous analysis values, as appropriate

Table 33: Pairwise Comparisons of Geometric Mean Titers Between Vaccination Groups, by Visit and Antigen – [Assay name]

Visit	Antigen	Comparison	p-value ^a	Adjusted p-value ^b
Visit 2 (Day 1)	gp120A244gD-D11	Full IHV01/A244 vs. Placebo	0.xx	0.xx
		Fractional IHV01/A244 vs. Placebo	0.xx	0.xx
		Full IHV01/A244 + ALFQ vs. Placebo	0.xx	0.xx
		Fractional IHV01/A244 + ALFQ vs. Placebo	0.xx	0.xx
		Full IHV01/A244 vs. Fractional IHV01/A244	0.xx	0.xx
		Full IHV01/A244 vs. Full IHV01/A244 + ALFQ	0.xx	0.xx
		Full IHV01/A244 vs. Fractional IHV01/A244 + ALFQ	0.xx	0.xx
		[Additional pairwise comparisons]	0.xx	0.xx
	[Additional antigens]			
[Additional visits or Peak]				

^aTwo-sided t-test used to compare log titer group means^bStep-down Bonferroni-Holm procedure used

Table 34: Collapsed Comparisons of Geometric Mean Titers, by Visit and Antigen – [Assay name]

Visit	Antigen	Full IHV01/A244 (N=X)		Fractional IHV01/A244 (N=X)		p-value ^a	ALFQ (N=X)		No ALFQ (N=X)		p-value ^a
		n	GMT (95% CI)	n	GMT (95% CI)		n	GMT (95% CI)	n	GMT (95% CI)	
Visit 2 (Day 1)	gp120A244gD-D11	xx	xx.x (xx.x, xx.x)	xx	xx.x (xx.x, xx.x)	0.xx	xx	xx.x (xx.x, xx.x)	xx	xx.x (xx.x, xx.x)	0.xx
	[Additional antigens]										
[Additional visits or Peak]											

Note: N = Number of participants in the Immunogenicity Population; n = Number of participants with available samples

^aTwo-sided t-tests used

Table 35: GEE Model to Evaluate the Longitudinal Immune Response and Relationship with Vaccine Dosage and Adjuvant – [Assay name]

Model Parameter	Value	Parameter Estimate	SE	p-value
Intercept	Intercept	XXX.X	XXX.X	X.XXX
Vaccine Dosage	Fractional Dose (reference)			
	Full Dose	XXX.X	XXX.X	X.XXX
Adjuvant	None (Reference)			
	ALFQ	XXX.X	XXX.X	X.XXX
Study Day	Day 0 (Reference)			
	Day 14	XXX.X	XXX.X	X.XXX
	Day 168	XXX.X	XXX.X	X.XXX
	Day 336	XXX.X	XXX.X	X.XXX
Dosage*Adjuvant Interaction	[All interaction levels]	XXX.X	XXX.X	X.XXX
		XXX.X	XXX.X	X.XXX

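### SAP 8.1 takes peak titre over every visit, so the pre-vaccination Day 0 sample can count as the peak response, mainly in placebo recipients and non-responders

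*SAP*

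**What the plan says.** On the primary immunogenicity variable, SAP 8.1 reports group GMTs by visit and also for "the per-participant peak across all visits". It then describes the week of peak response by group, without testing, and adds: "If, by chance, there are equivalent peak responses at two visits, the first will be considered the peak".

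Day 0 falls within this definition:

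- SAP 4.7: "Humoral responses will be assessed by HIV-specific binding and neutralizing antibody assays at Days 0, 14, 168, and possibly at Day 336".
- SAP Table 2 makes Day 0 Visit 1 and schedules a binding-antibody sample then. The Table 32 shell has a baseline (Day 0) row.
- SAP 3.3 defines baseline as the last value before vaccination.
- Neither document limits the peak to visits after vaccination.

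SAP 3.3 also puts titres on a two-fold grid, sets values below the limit of detection (LOD) to half that limit, and averages replicates geometrically where there are any.

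Peak can enter the between-group shells (Tables 32-34) through a bracketed row, "Additional visits or Peak". Week of peak is Table 40. Separately, Protocol 10.2.1 describes durability as the decline in log10 "IgG from peak to 6- and 12-months post vaccination".

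**The concern.** A peak response to vaccination cannot come before the vaccination. A programmer following SAP 8.1 as written would nevertheless include the Day 0 value in the maximum. There are two separate effects.

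1. **Peak GMT.** When Day 0 is strictly the highest value, it replaces the highest post-vaccination value. This happens mostly in people whose titre does not rise, so it lifts the placebo peak and narrows any active-versus-placebo difference in peak.
2. **Week of peak.** On a two-fold grid a stable titre often ties across visits, and an undetectable titre ties at every visit. The tie rule assigns these profiles to Week 0. It cannot change peak GMT, because tied values are equal.

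SAP 8.2 applies a similar process to the other assays, so the definition carries beyond plasma IgG.

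**Working it through.** **What the documents supply.** They give three or four binding-antibody visits, a two-fold grid, the first-visit tie rule and 16 placebo recipients. They do not give the within-person visit-to-visit SD, the decline rate, the share below the LOD or the number of replicates. The only SD (SAP 4.4.1, about 0.5-1.0 for log titre in a group) is not a visit-to-visit SD. The plan states no share of peaks at Day 0, so there is no figure to reproduce on that point.

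**Share of placebo peaks at Day 0 with no ties and no trend.** Each visit is equally likely to be highest: 1/4 = 25% with four visits, 1/3 = 33% with three. Of 16 people, that is about 4 or 5.

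**With the two-fold grid and the tie rule.** I simulated 300,000 placebo profiles per scenario. Each had one reading per visit, floored to the grid, with the first maximum taken as the peak. Assumed within-person SD: 0.2-0.3 log10 (0.2/0.301 = 0.66 to 0.3/0.301 = 1.0 log2). Waning means 0, 0, -0.1, -0.2 log10 at Days 0, 14, 168 and 336.

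| Visits | Trend | Peak at Day 0 | Peak GMT above a post-vaccination peak | In log10 |
|---|---|---|---|---|
| 4 | flat | 40-47% | 9-13% | log10(1.09) to log10(1.13) = 0.04-0.05 |
| 4 | waning | 49-59% | 15-21% | log10(1.15) to log10(1.21) = 0.06-0.08 |
| 3 (no Day 336) | flat or waning | 48-62% | 14-26% | log10(1.14) to log10(1.26) = 0.06-0.10 |

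In the four-visit runs Day 0 was strictly highest in 11-21% of profiles. Those profiles alone drive the rise in GMT; the rest of the Day 0 share comes from ties.

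**Wider assumptions, four visits.**

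- Flat titres: 74%, 55%, 40% and 34% at SD 0.25, 0.5, 1.0 and 1.5 log2.
- Decline of 1 log2 per year: 87% down to 43% over the same SDs.
- With the untied case, the range is about 25-87%.
- If a share f is undetectable throughout, the total is f + (1 - f) x p. For example, f = 0.2 and p = 0.45 give 0.2 + 0.8 x 0.45 = 56%.
- Even with a true share of 50%, the 95% binomial range in 16 people is 4 to 12.

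**Active groups.** With an assumed Day 14 rise of 3 log2 (eight-fold) or more, and SD 0.5-1.0 log2, about 0-3% peak at Day 0.

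**Scale against the plan's own yardstick.** SAP Table 4 gives 1.02 SD as detectable for 16 v 16 at 80% power; a noncentral-t calculation gives 1.024, so it reproduces. With SD 0.5-1.0, and taking the log as base 10 (an assumption), that is 0.51-1.02 log10. A bias of 0.04-0.10 is then 0.04/1.02 = 4% to 0.10/0.51 = 20% of the detectable difference.

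**What the fix removes.** With flat titres, the placebo peak sits above the mean titre by 0.51 log2 over four visits and 0.42 over the three post-vaccination visits (SD 0.5), or 1.03 and 0.85 (SD 1.0). About 0.42/0.51 = 82% to 0.85/1.03 = 83% of the shift remains, because any maximum of noisy values lies above their mean.

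**The case against.** The case for leaving the text alone has real force.

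- **The share is not in the documents.** A reader might infer that about half of placebo peaks will fall before vaccination. That does not follow from the two rules alone; it depends on assay variability, waning, undetectable values and replicates, none of which is given. Averaging replicates would break some ties. This stands, and is why the size is stated as an assumption with a range.
- **Peak is not clearly tested.** A reader might infer a formal peak comparison with placebo. SAP 8.1 plans tests at targeted time points without naming peak among them, and peak appears in the shells only as a bracketed option. A test is possible but not committed to.
- **The bias is small and conservative.** It works against finding a vaccine effect. Both collapsed contrasts (dose and ALFQ) exclude placebo, and Protocol 12.1 says placebo is there mainly for blinding. This stands.
- **Durability.** A reader might infer that decline from peak will start before vaccination. SAP 8.1 measures durability by incremental AUC. Decline from peak is only in Protocol 10.2.1, which does not say that its peak includes Day 0.
- **Week 0 in placebo is informative.** It can correctly signal no post-vaccination rise, so Table 40 would not be meaningless for placebo.

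These points limit the consequence. None gives a reason for a pre-vaccination sample to count as a response to vaccination.

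**Conclusion.** The point holds as a minor defect of definition. Taken literally, SAP 8.1 lets Day 0 be the peak, and a substantial share of placebo and non-responder peaks would fall there. The 40-60% figure rests on a within-person SD of 0.2-0.3 log10, single readings on a two-fold grid, and flat or slightly waning titres; the 9-26% rise in placebo peak GMT rests on the same assumptions. The tie rule matters only for the untested week of peak.

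The documents do not support a stronger reading in which the main immunogenicity comparisons are compromised. Visit-specific GMTs and AUC do not use the peak, and the dose and ALFQ contrasts are essentially unaffected if active recipients respond clearly.

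**What to change.** In SAP 8.1, define the peak as the maximum over post-vaccination visits (Days 14, 168 and, if assayed, 336), for both peak GMT and week of peak. Keep the Day 0 GMT as its own row in Table 32. If the Protocol 10.2.1 decline from peak is calculated, use the same definition there.

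The cost is one phrase in the SAP and no new data. There is a small downside. The peak still sits above the mean titre, as shown in the working. With the tie rule kept, about 48-62% of flat placebo profiles (SD 1.0 down to 0.5 log2, three post-vaccination visits) would be labelled as peaking at Day 14. A footnote to Table 40 should say that week of peak in placebo reflects the tie rule as well as any response.

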12. STATISTICS

12.1. Analysis Overview

This study intends to descriptively characterize safety and immune responses following delayed boosting of individuals previously vaccinated with a late boost of AIDSVAX®B/E with or without ALVAC in the RV306 protocol. Statistical analysis considers targeted enrollment into the following 5 groups:

- Placebo (n=16)
- Group 1: IHV01 and A244/AHFG Full Dose (n=16)
- Group 2: IHV01 and A244/AHFG Fractional Dose (n=16)
- Group 3: IHV01 and A244/AHFG Full Dose + ALFQ (n=16)
- Group 4: IHV01 and A244/AHFG Fractional Dose + ALFQ (n=16)

Collapsed comparisons of interest include full dose vs. fractional dose (Groups 1+3 vs. Groups 2+4) and effect of ALFQ (Groups 1+2 vs. Groups 3+4). The placebo group is included primarily for purposes of blinding safety and immunogenicity assessments, including blinded samples for the set of immunology assays. The main interest is in determining the safety of IHV01 (FLSC), A244/AHFG and ALFQ as well as whether immunologic differences can be detected between the 4 antigen-containing regimens. Response rates and, where applicable, titer level distributions with appropriate summary statistics will be estimated for each immunologic assay performed. The study will evaluate a series of cellular, humoral and mucosal immune assays. In many cases, trial specimens will be used to further evaluate the practicality of sampling, specimen processing and storage procedures combined with assay performance characteristics. As this study will enroll only participants who had completed the RV306 study, participant data from RV306 will be used in conjunction with data collected in this study to provide a more in-depth analysis of the effect of delayed boosting.

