4. INVESTIGATIONAL PLAN

4.1. Overall Study Design and Plan

This is a Phase I randomized, double-blind, placebo-controlled clinical trial to define the safety and immunogenicity of IHV01/A244 with and without ALFQ at a full dose and at a fractional dose in a late boost setting for participants who had previously received the AIDSVAX®B/E with or without ALVAC in RV306. Participants will be randomized to receive 2 intramuscular (IM) injections, either IHV01/A244 (target of n=64 total, with n=16 per study arm) or saline placebo (target of n=16 total, with n=4 per study arm), into the same quadriceps muscle at Day 0. Half of the IHV01/A244 recipients will receive the full IHV01 (FLSC) dose (Groups 1 and 3) while the other half (Groups 2 and 4) will receive a fractional dose of each vaccine, which is one fifth of the standard dose. Groups 3 and 4 will also receive ALFQ. Enrollment will be sequential, with Groups 1 and 2 accruing first with a 2:2:1 ratio of full dose to fractional dose to placebo, followed by enrollment into Groups 3 and 4 with the same targeted allocation ratios. After the first 8 participants are enrolled across Groups 1 and 2, the Safety Monitoring Committee (SMC) will review 7 days of safety data from these participants to determine whether enrollment can continue. Enrollment into Groups 1 and 2 will continue unrestricted after any safety concerns raised by the SMC are addressed and the Sponsor gives their approval for the continuation of enrollment. Enrollment into Groups 3 and 4 will commence after enrollment into Groups 1 and 2 has been completed, the SMC has reviewed 7 days of safety data from all Group 1 and Group 2 participants, and the Sponsor gives their approval. Enrollment into Groups 3 and 4 will follow a similar approach with an SMC review of 7 days of safety data from the first 8 participants enrolled across both groups, and Sponsor approval before enrollment can continue unrestricted in Groups 3 and 4.

Participants will receive 2 IM injections, either IHV01/A244 (n=64) or saline placebo (n=16) at Day 0, and return for follow up at 1, 7, 14, 168, and 336 days after vaccination (protocol version 5.0, section 7.2). Figure 1 gives a schematic of the study design, with the RV306 groups shown on the left and the RV546 groups on the right.

Figure 1: Study Schematic

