Study arms are given below in Table 1. For analysis purposes, participants will be grouped by vaccination regimen received, so placebo participants will be considered the fifth Vaccination Group.

Table 1: Study Arms

Group #	Intervention	Control
Group 1	16 Full IHV01/A244	4 placebo
Group 2	16 Fractional IHV01/A244	4 placebo
Group 3	16 Full IHV01/A244 + ALFQ	4 placebo
Group 4	16 Fractional IHV01/A244 + ALFQ	4 placebo

The schedule of events is given in Table 2 below, for reference.

Table 2: Schedule of Events

Visit	S1	1	2	3	4	5	6 (Exit)	7
Visit Day	-45 to -16	0	1	7	14	168	336	Post Database Lock
Visit Week		0	1	1	2	24	48	
Visit Month		0			0.5	6	12	
Visit Window			+2d	-/+2d	-2/+3d	-/+7d	-/+7d	
Clinical								
Informed Consent (Main, Storage/Future Use, Genetic, and Optional Procedures)	X							Final Results and Unblinding ⁵
Test of Understanding	X							
Enrollment and Randomization		X						
Vaccination		X						
Vital Signs ⁸ and Physical exam ¹	X	X		X	X	X	X	
Medical History & Concomitant Medications	X	X		X	X	X	X	
Adverse Event Documentation (AE, SAE, AESI)		X	X	X	X	X	X	
Diary Card		X	X	X				
HIV Risk Assessment/Risk Counseling	X	X			X	X	X	
Pregnancy Test & Pre/Post Counseling	X	X			X	X	X	
Urinalysis (blood, protein and glucose)	X	X	X	X	X	X	X	
CBC w/ diff & CD4	2	2	2	2	2	2	2	
Creatinine, ALT/AST	3.5			3.5	3.5	3.5	3.5	
Syphilis and Hepatitis B Serology	3.5							
HIV Testing & Pre/Post Counseling	6				6	6	6	
Optional Procedures								
Mucosal Secretions ^{2,7} ; Plasma LH and FSH (cervical secretions only)		X			X	X	X	
STI Testing ⁷	X							
Vaginal ^{2,7} and/or rectal ^{3,7} and/or penile ⁷ swab for microbiome and proteome		X			X	X	X	
Endocervical Cytobrush/swab ^{2,7}		X			X	X	X	
Pap Smear, if none available in last two years ⁷	X							

Visit	S1	1	2	3	4	5	6 (Exit)	7
Visit Day	-45 to -16	0	1	7	14	168	336	Post Database Lock
Visit Week		0	1	1	2	24	48	
Visit Month		0			0.5	6	12	
Visit Window			+2d	-/+2d	-2/+3d	-/+7d	-/+7d	
Sigmoid Biopsy ^{3,7}					X			
Lymph Node Biopsy					X			
Leukapheresis ⁴					X (10ml)			
Safety Tests for Biopsy or Leukapheresis (up to max possible volume) ¹⁰					20			
Research								
HIV Binding Antibody		SP			SP	SP	SP	
HIV Neutralizing Antibody Assays		6			6	6	6	
Functional Antibody Assays		SP			SP	SP	SP	
B-Cell Analysis ⁶		30		30	30	30	30	
Multiparameter Flow Cytometry		20			20	20	20	
Innate Cell Analysis		20	20	20	20	20	20	
Transcriptomics		20	20	20	20	20	20	
Additional Immunogenicity Testing ⁶		30		30	30	30	30	

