5.8. Multiple Comparisons/Multiplicity

For comparisons of safety outcomes, 5%-level two-sided tests will be made. Some of these may be implicit comparisons based on the overlap of group-level confidence intervals (i.e. non-overlapping 95% CIs mean rejecting the null hypothesis of no difference between groups at the 0.05-level).

To compare primary immunogenicity outcomes (antigen-specific plasma IgG binding responses, as measured by log AUC over time) across all groups, 5%-level two-sided tests will be used. When differences are found, pairwise comparisons between vaccination groups will be made using the Bonferroni-Holm step-down procedure [1] and a 5% significance threshold for the adjusted p-values; if no difference is found across all groups, no pairwise comparisons will be made. Collapsed comparisons will be considered separately and will be made with 2.5%-level two-sided tests, even when no pairwise differences are observed.

Further exploratory comparisons for immunogenicity endpoints across all groups will be adjusted for multiplicity by a Bonferroni adjustment: multiplying p-values by the number of assays in the same set (e.g. across antigens for a given antibody test; see Section 3.2.2 for sets of assays). Then a similar process as above will be followed, with pairwise comparisons following a significant overall test and Bonferroni-Holm step-down procedure (with a 5% significance level) to account for the multiple pairwise tests.

These adjustments are intended to improve control of the type-I error across comparisons for the same outcome measure and time point (e.g. Geometric Mean Titers (GMTs) for gp120A244 plasma IgG binding at Day 14) rather than across outcome measures and/or time. This level of type-I error control will still allow for exploratory findings that would be assessed further in future studies.

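### The ANOVA that gates the pairwise tests includes placebo, so a vaccine response alone can open it; in the exploratory sets the correction for number of assays then stops protecting regimen-versus-regimen claims

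*SAP*

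**What the plan says.** Protocol 12.1 gives the immunologic interest as "whether immunologic differences can be detected between the 4 antigen-containing regimens" and says placebo is there mainly to support blinding. Protocol 12.2.4 also lists all active versus placebo as a comparison of interest.

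SAP 4.1 pools the placebo recipients: "placebo participants will be considered the fifth Vaccination Group". The planned sizes are "target of n=64 total, with n=16 per study arm" for vaccine and "target of n=16 total, with n=4 per study arm" for placebo, so the analysis has five groups of 16.

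For the primary endpoint, SAP 8.1 starts with the overall test: "First, group GMTs will be compared across all vaccination groups via ANOVA (null hypothesis that all groups share the same GMT) at the 5%-level". If it is significant, "pairwise comparisons via 2-sided t-tests and the Bonferroni-Holm step-down procedure will be made and a 1% significance threshold will be applied". SAP 5.8 describes the same gate ("if no difference is found across all groups, no pairwise comparisons will be made") but puts the threshold for Holm-adjusted p-values at 5%. The shells for Tables 29, 32 and 37 carry one overall p-value across five columns, one of which is placebo.

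For exploratory endpoints, SAP 5.8 adjusts the comparison across all groups by "multiplying p-values by the number of assays in the same set". The pairwise tests that follow get Holm at 5% within the assay, and no assay factor is stated for them.

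The two collapsed comparisons (dose and ALFQ) use active recipients only, are tested at 2.5% each, and do not depend on the gate.

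**The concern.** The null hypothesis of the gate is that all five groups share one mean. It is false as soon as vaccination raises antibody above saline, even if the four regimens are identical. Two things follow.

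First, the overall p-value in Tables 29, 32 and 37 mixes two questions: whether vaccine differs from saline, and whether the regimens differ. No single test in the plan addresses the second alone.

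Second, in an exploratory set the assay-count factor reaches the regimen-versus-regimen tests only by making the gate harder to pass. If placebo opens the gate, that factor no longer acts on those tests. SAP 8.1 says the testing is meant to help choose responses for study in later trials, so false regimen differences could be carried forward.

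**Working it through.** **Inputs.** Five groups of 16 (SAP 4.1); gate at 5% and Holm over the 10 pairs (SAP 5.8, 8.1). Two inputs are assumptions because the documents do not give them. One is the distance d, in SD, by which placebo lies below four identical regimens. The other is the number of assays M in an exploratory set. I take M = 4 (Protocol 10.2.1 names four binding antigens) and M = 11 (its Tier 2 pseudovirus panel). Log titers are taken as normal with equal SD, as in SAP 4.4.1.

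**The plan's own figure.** Power of a two-sample t-test comes from the noncentral t with noncentrality d·√(n1·n2/(n1+n2)). For 16 versus 16 and d = 1.02 this is 1.02 × √8 = 2.885 on 30 df, giving 79.7% power. Solving for d at 80/85/90% power:
- 64 versus 16: 0.793/0.848/0.917 (SAP Table 4: 0.79/0.85/0.92)
- 32 versus 32: 0.711/0.761/0.823 (0.71/0.76/0.82)
- 16 versus 16: 1.024/1.095/1.185 (1.02/1.09/1.18)

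Table 4 reproduces.

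**The gate.** With four means at 0 and placebo at −d, the grand mean is −d/5. The noncentrality of the five-group ANOVA is 16 × [4(d/5)² + (4d/5)²] = 16 × 0.8d² = 12.8d², on 4 and 75 df. At d = 1 this is 12.8, and the test is significant at 5% in 80.3% of trials. At d = 0.79, the plan's detectable difference for active versus placebo, it is 57%. An ANOVA of the four regimens alone (3 and 60 df) has noncentrality 0 and stays at 5%.

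**Within one endpoint.** In simulation (100,000 replicates, regimens identical), the chance of any false regimen-versus-regimen claim is 1.9-4.1% at the 5% Holm threshold and 0.5-0.9% at the 1% threshold, for d from 0 to 3. Holm controls this without help from the gate.

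**Exploratory sets.** The per-assay chance of a false regimen claim shows what the assay factor does. Going from no factor to a factor of 4 lowers it from 1.9% to 0.8% at d = 0, from 3.1% to 3.0% at d = 1, and not at all at d = 2 (4.0% both times). Across M independent assays the chance of at least one is 1 − (1 − p)^M. At d = 1 with M = 4 it is 1 − (1 − 0.0303)⁴ = 11.6%; at d = 2 it is 1 − (1 − 0.0399)⁴ = 15.0%. Simulation gives the values for correlated assays and for M = 11. Ranges run from correlation 0.8 to independence.

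| d (SD) | Gate open at 5% | Gate open after factor 4 | Any false regimen claim, 4 assays | Same, 11 assays |
|---|---|---|---|---|
| 0 | 5% | 1.3% | 2-3% | 2-4% |
| 0.5 | 24% | 10.5% | about 5-7% | about 5-12% |
| 1 | 80% | 61% | 8-12% | 13-27% |
| 1.5 | 99.4% | 97% | 9-15% | 17-36% |
| 2 | >99.9% | >99.9% | 10-15% | 18-38% |

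With a four-regimen gate carrying the assay factor, the same chance is about 5% or less at every d.

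**The case against.** The strongest reply is that the regimen question is already tested without placebo. The dose and ALFQ collapsed comparisons are active-only, ungated and run even when no pair differs (SAP 5.8 and 8.1; Tables 31 and 34). The GEE model in SAP 8.2 has dosage, adjuvant and their interaction, with no placebo level (Table 35). This stands: a reader might infer that dose and ALFQ go untested, and the documents do not support that.

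A reader might also infer that error is inflated in the primary analysis. It is not, because Holm over the 10 pairs controls it within each endpoint.

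Nor do the documents show that the overall test will be significant for nearly every antigen and visit. They give no vaccine-versus-placebo effect for any assay, and Protocol 5 describes titers falling over the months after boosting. The SD of 0.5 to 1.0 in SAP 4.4.1 is for log IgG titer and does not carry over to neutralization or cellular assays. At 0.5 SD with 4 assays the excess is small. To say that the assay correction is defeated outright would be too strong.

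Placebo also has a legitimate place. Protocol 12.2.4 asks for active versus placebo, and the SAP's only stated tests of it on the immunogenicity endpoints are the five-group test and the placebo pairs. The table footnotes say plainly that the ANOVA covers all vaccination groups.

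Finally, SAP 5.8 limits its error control to one outcome at one time point and accepts exploratory findings. That lowers the severity. It does not remove the point: the same section specifies a correction across assays, and on its plain wording that correction does not reach the regimen-versus-regimen tests.

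**Conclusion.** The point holds in a limited form. The five-group ANOVA is not an overall test of the four regimens, and a vaccine response of about 1 SD or more will usually make it significant. For the primary endpoint the consequence is interpretive only.

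The substantive weakness is in the exploratory sets. Once placebo opens the gate, regimen-versus-regimen claims carry little or no correction for the number of assays. The loss is nil with no vaccine effect, modest at 0.5 SD and near total from 1.5 SD.

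The size depends on the assumed d, M and correlation between assays. It also rests on reading the assay factor as applying to the overall p-value only; if the sponsor means it to apply to the pairwise p-values as well, this part falls away and the SAP should say so. Seroconversion (Table 37) has the same structure, but its rates were not computed.

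**What to change.** In SAP 5.8 and 8.1:
- Gate the six regimen-versus-regimen pairs on an ANOVA of the four active regimens (a four-group exact test for seroconversion), with Holm over those six.
- For exploratory sets, multiply that four-regimen p-value by the number of assays.
- Report the four-regimen p-value in Tables 29, 32 and 37.
- Report the four regimen-versus-placebo comparisons as a separate Holm family.
- Leave the collapsed comparisons as they are.
- Reconcile the 1% (8.1) and 5% (5.8) Holm thresholds.

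A minimal alternative is to keep the five-group gate and also multiply the exploratory pairwise p-values by the number of assays. With independent assays this holds the chance of a false regimen claim at 2.5-4.7%, but it costs more power.

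**Cost.** SAP wording and table footnotes; no new data or participants. Power figures are for one regimen raised by 1.02 SD. Primary power to find any regimen pair, with placebo 1.5 SD below the other regimens, changes by about 1 point: 77.4% to 76.5% at the 5% threshold, 53% to 54% at 1%. Exploratory power per assay at the 5% threshold falls from 78% to 65% with 4 assays (57% under the minimal alternative) and to about 51% with 11. That is the price of the assay correction the SAP already states. The placebo comparisons become a second 5% family.
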